5.3 Informed Consent Procedures

We are requesting a waiver of informed consent for recruitment/screening purposes only. This will allow us to create recruitment mailing lists that can target the most-likely-to-be-eligible populations, and not waste resources and other patients' time advertising the study to patients who won't be eligible to participate.

We will obtain informed consent prior to beginning any data collection study procedures that will be maintained for analysis. Informed consent will take place at the beginning of the appointment that includes the subject's in-person screening and (if still eligible) baseline assessments. The study coordinator, project manager, or other approved researcher administering the screening and baseline measures will obtain informed consent at this time. We will not be enrolling anyone with impaired decision making ability who requires the use of a legally authorized representative.

All study personnel will be trained in human subjects protections requirements as required by R&D (e.g. Privacy Policy & HIPAA training), and the PI or Project Manager will train any other study team members how to appropriately obtain informed consent as needed.

5.4 Inclusion/Exclusion Criteria

Inclusion criteria: All participants (both GW and non-GW Veterans) must meet criteria for CMI, defined as self-report of at least two of the following 1) fatigue that limits usual activity; 2) musculoskeletal pain involving two or more regions of the body; 3) cognitive symptoms (memory, concentration, or mood disturbances).¹³ GW Veterans must have been deployed to the GW theater of operations between 8/1990 – 8/1991,

have symptoms of CMI that began after 8/1990, lasted at least 6 months, and are present at the time of the interview.

Exclusion criteria: At baseline, the MINI psychiatric interview⁷⁵ will determine psychiatric exclusion criteria: 1) current psychotic disorder; 2) current bipolar affective disorder with mania; 3) current suicidal or homicidal ideation. Additional exclusion criteria include a chart diagnosis of borderline or antisocial personality disorder or prior *formal* participation in MBSR or CDSMP. We will include subjects with the entire range of alcohol SUD (defined by the MINI), but exclude those for whom alcohol use poses a safety threat (defined as current drinking and a past-year history of alcohol-related seizures or delirium tremens). We will also exclude current DSM-V substance use disorder other than cannabis or nicotine, as well as inpatient psychiatric admission within the past month. Medication, supportive individual or group counseling, case management, and self-help programs will be allowed and assessed as potential covariates. As of July 2020, participants must have the required technology in order to participate in VVC intervention groups.

5.5 Study Evaluations

(B=baseline; M=midway through treatment; P=post-treatment; 3=3-months post-treatment; 6=6-months post-treatment)

Measure/Data Collection Tool	Assessment	Purpose/Variable that the tool measures
Study Sample Description Data (describes subject population and generalizability of results)		
Demographic Information	B	Sample description, blocking (gender), moderators
Life Events Checklist (LEC)	B	Sample description; trauma history
Deployment Risk and Resilience Inventory (DRRI)	B	Wartime exposures
Rome III – IBS	B	Sample description, to indicate prevalence of Irritable Bowel Syndrome in sample
Eligibility Evaluation (inclusion/exclusion criteria)		
Chronic Multi-Symptom Illness (CMI) Questionnaire	B	Sample description, eligibility evaluation
MINI International Neuropsychiatric Interview V-5 (DSM-V)	B	Sample description, eligibility evaluation, SUD classification (possible moderator)

Medical history interview (seizures, delirium tremens)	B	Sample description; eligibility evaluation
Tracking		
Contact form	B, P, 3, 6	Updating subject contact information; retention
Primary Outcomes		
Short Form McGill Pain Questionnaire (SF-MPQ-2) total score	B, M, P, 3, 6	Pain
General Fatigue subscale of the Multidimensional Fatigue Inventory (MFI)	B, M, P, 3, 6	General fatigue symptoms
Cognitive Failures Questionnaire (CFQ)	B, M, P, 3, 6	Concentration and memory disturbances
Client Satisfaction Questionnaire (CSQ-8)	P, 6	Satisfaction with the group (MBSR or aCDSMP)
Qualitative Interviews	P	Data merging and mixed methods techniques, used to analyze patient impressions of, and levels of satisfaction with, MBSR and aCDSMP
Secondary Outcomes		
Patient Health Questionnaire (PHQ-9)	B, P, 3, 6	Depressive symptoms
PTSD Checklist – Civilian Version (PCL-C)	B, P, 3, 6	Post-traumatic Stress Disorder symptoms
SF-12 (Mental and Physical Component Summary Scores)	B, P, 3, 6	Health-related quality of life
Drug Abuse Screening Test (DAST) for drug use other than alcohol or tobacco	B, P, 3, 6	Drug use: frequency and severity
NIH Patient Reported Outcome Measures Information System (PROMIS) for Alcohol Use and Negative Consequences, short form	B, P, 3, 6	Substance Use Disorder (SUD) symptom severity for alcohol
NIH Patient Reported Outcome Measures Information System (PROMIS) for Gastrointestinal	B, P, 3, 6	Gastrointestinal Symptoms, including IBS

Distress		
Potential Mediators		
Pain Self-Efficacy Questionnaire (PSEQ)	B, M, P, 3, 6	
Coping Strategies Questionnaire (CSQ)	B, M, P, 3, 6	
Five-Facet Mindfulness Questionnaire (FFMQ-15)	B, M, P, 3, 6	Dispositional mindfulness, and mindfulness subscales: Observing, Describing, Acting with Awareness, Nonjudging and Nonreactivity to inner experiences
Self-Compassion Scale (short form)	B, M, P, 3, 6	Self-compassion
Experiences questionnaire	B, M, P, 3, 6	Decentering
Potential Moderator (in addition to demographic info)		
Credibility/Expectancy Questionnaire	M	Participants' belief in treatment rationale/Treatment credibility and positive expectancy
VA Health Care		
CPRS review for engagement in other treatments since baseline	6	Other care received during study as possible moderator

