Human Subjects Protocol

VA Puget Sound IRB

[MIRB 00873] A Randomized Clinical Trial of Group Interventions for Veterans with Chronic Multi-Symptom Illness

Funding Agency: VA HSR&D

Principal Investigator: [name]

Version 10; 7/7/2021

Abstract

The study will recruit and randomize up to 308 participants. Half (n=154) of these will be Gulf War Veterans who meet criteria for Chronic Multi-Symptom Illness (CMI), and the other half (n=154) will be Veterans from other periods of service who also meet criteria for CMI. Half of the Gulf War Veterans (n=77) and half of the non-Gulf War Veterans (n=77) will be randomly assigned to the Mindfulness-Based Stress Reduction (MBSR) group, and the other 154 participants (77 Gulf War Veterans, 77 non-Gulf War Veterans) will be randomly assigned to the augmented Chronic Disease Self-Management Program (aCDSMP) group. As of July 2020, these groups will be conducted remotely using the VA's Video Connect software, due to the restrictions resulting from the COVID-19 virus. Each of the group sessions are 2.5 hours long, and they meet once a week for 8-weeks, as well as once on a Saturday for 4 hours (between Week 6 and 7). As of July 2020, we will no longer be including Saturday sessions, given the difficulties of doing so in a remote learning format. Each cohort will randomize 30 subjects or until one intervention reaches 18 randomized participants, whichever occurs first. As of July 2020, groups are capped at 10 participants each, or 19 subjects randomized per cohort; this cap reflects ideal group sizes for the remote learning format.

Data will be collected from subjects during five assessments while they are enrolled in the study: 1) at Baseline, which will take place within 6 weeks prior to beginning MBSR or aCDSMP; 2) at "Midpoint," between Week 4 and Week 5; 3) at "Post," within a month following the completion of the group series; 4) at 3-months after the group ended; and 5) at 6-months after the group ended.

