At each of these assessments except the Midpoint, researchers will provide and administer self-report measures to the participants using a VA computer to assess changes in the following symptoms and attitudes over time and between the two study arms: pain, fatigue, cognitive failures, depression, PTSD, health- and mental-health-related quality of life, drug use, alcohol use and negative consequences, gastrointestinal distress, mindfulness, self-compassion, and decentering. These assessments can be completed both in person or by phone, as of March of 2020 all assessments will be completed by phone because of COVID-19 restrictions. At the Midpoint, participants complete a pen-and-paper set of questionnaires assessing potential mediations (e.g. mindfulness and self-efficacy) and primary endpoints, which will allow mediation analyses to be performed in the future.

At the Post Assessment, a qualitative interview will be conducted with Gulf War veterans to explore impressions of, and satisfaction with, the two different treatments (MBSR and aCDSMP). List of Abbreviations

CMI – Chronic Multi-Symptom Illness

GW – Gulf War

GWS – Gulf War Syndrome

MBSR – Mindfulness-based Stress Reduction

aCDSMP – adapted Chronic Disease Self-Management Program

CPRS – Computerized Patient Record System (electronic medical record)

PROMIS – Patient-reported Outcome Measures Information System

VVC- VA Video Connect

Contents

Protocol Title:.....	5
1.0 Study Personnel.....	5
2.0 Introduction.....	5
3.0 Objectives.....	8
4.0 Resources and Personnel.....	8
5.0 Study Procedures.....	10
5.1 Study Design.....	10
5.2 Recruitment Methods.....	14
5.3 Informed Consent Procedures.....	16
5.4 Inclusion/Exclusion Criteria.....	17
5.5 Study Evaluations.....	17
5.6 Data Analysis.....	20
5.7 Withdrawal of Subjects.....	21
6.0 Reporting.....	21
7.0 Privacy and Confidentiality.....	21
8.0 Communication Plan.....	22
9.0 References.....	23

Protocol Title: A randomized clinical trial of group interventions for Veterans with Chronic Multi-Symptom Illness

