3.0 Objectives

The purpose of this study is to determine whether there is clinical evidence to support the use of Mindfulness-Based Stress Reduction as a treatment for Veterans with Chronic Multi-Symptom Illness: pain, fatigue, and cognitive or mood disturbances.

Hypothesis One (re: outcomes): Participants randomized to CDSMP will derive benefit for the primary outcomes, but with smaller effects than the participants randomized to MBSR. We hypothesize that Veterans randomized to MBSR will report significantly greater reduction in each of the three primary outcome measures (pain, fatigue and cognitive failures) at 6-month follow-up as compared to aCDSMP.

Hypothesis Two (re: acceptability): MBSR will be an acceptable and satisfactory program for Veterans with CMI, as indicated by attendance rates, a self-report measure of satisfaction, and qualitative interviews. We hypothesize that Veterans with CMI randomized to MBSR will report greater satisfaction with care than their peers randomized to CDSMP.

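### Section 5.5 labels two measures taken after randomisation, Midpoint credibility and other care since baseline, as possible moderators; an interaction with either can appear without true effect modification

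*Combined protocol and SAP*

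**What the plan says.** The measures table in Section 5.5 places the Credibility/Expectancy Questionnaire under "Potential Moderator (in addition to demographic info" and schedules it at M only. The Abstract puts the Midpoint assessment "between Week 4 and Week 5" of the group series. The same table lists a "CPRS review for engagement in other treatments since baseline", done at 6 months, with the purpose "Other care received during study as possible moderator".

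The other named moderators, demographics and the substance use disorder (SUD) classification from the MINI, are collected at baseline, "which will take place within 6 weeks prior to beginning MBSR or aCDSMP" according to the Abstract. Hypothesis One in Section 3.0 concerns three outcomes, "pain, fatigue and cognitive failures) at 6-month follow-up as compared to aCDSMP", so the care review closes at the same time point as those outcomes.

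Three other places bear on the point:
- Section 5.4 says: "Medication, supportive individual or group counseling, case management, and self-help programs will be allowed and assessed as potential covariates". It gives no time point.
- The Abstract describes the Midpoint forms as "assessing potential mediations (e.g. mindfulness and self-efficacy) and primary endpoints, which will allow mediation analyses to be performed in the future".
- Section 5.6 gives the sample size and says when the data will be analysed. It specifies no moderator model and does not separate moderators measured before assignment from those measured after it.

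**The concern.** A moderator analysis asks whether the effect of MBSR against aCDSMP differs between kinds of participant. Randomisation protects that comparison within levels of a variable only if assignment cannot influence the variable.

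Neither variable meets that condition. At Midpoint, participants rate the credibility of the programme they were assigned to, after about half of it, so the rating can reflect both the programme and how they have fared so far. Other care taken up during the study can be a response to symptoms that did or did not improve. Participants in the two arms with the same credibility score, or the same amount of other care, may then differ in prognosis.

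At stake is the reading of an exploratory interaction: part or all of it could be prognosis or early response instead of effect modification. Credibility has no baseline value in the schedule, so no score taken before assignment can stand in for it.

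**Working it through.** **The plan's own figure.** For d = 0.50, two-sided alpha 0.05 and 80% power, the normal approximation gives 2 × (1.960 + 0.842)² / 0.50² = 62.8, so 63 per arm. The two-sample t-test gives 63.8, so 64, as Section 5.6 states. Then 64 × 1.2 = 76.8, so 77 per arm and 154 in total. The point does not dispute this figure; 64 per arm is only used below.

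**Timing, from the documents.**
- Credibility is rated after about 4 of 8 weekly sessions.
- The care window runs from baseline (up to 6 weeks before the first session), through the group (8 weeks, or 7 from first to last session), to about 26 weeks after the group ends.
- Share of the window after the first session, with baseline as early as allowed: (8 + 26)/(6 + 8 + 26) = 34/40 = 85.0%, or (7 + 26)/(6 + 7 + 26) = 33/39 = 84.6%. A later baseline raises it. So roughly 85% or more of the window follows the start of the assigned group.

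**Illustration of a false interaction. All inputs except n = 64, alpha and d are assumed.** Outcome and variable each have SD 1 within arm. The true effect is 0.50 for everyone. Arm means of the variable are equal. The within-arm correlations of the variable with outcome are r1 and r0.

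Expected interaction coefficient: r1 − r0. Apparent effect at +1 and −1 SD: 0.50 ± (r1 − r0). Approximate standard error: √[(1 − r1²)/n + (1 − r0²)/n].

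For r1 = 0.5, r0 = 0.3, n = 64: SE = √[(0.75 + 0.91)/64] = 0.161; 0.20/0.161 = 1.24; rejection ≈ P(Z > 1.96 − 1.24) ≈ 0.24. The noncentral t gives 0.225 and simulation (20,000 trials) gives 0.229.

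| r1, r0 | Apparent effect at +1 / −1 SD | Rejection, 64 per arm | Rejection, 128 per arm |
|---|---|---|---|
| 0.3, 0.3 | 0.50 / 0.50 | 5% | 5% |
| 0.4, 0.3 | 0.60 / 0.40 | about 9% | 13–14% |
| 0.5, 0.3 | 0.70 / 0.30 | about 23% | 40–42% |

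The 128 per arm is 308/2/1.2 = 128.3, assuming the same attrition allowance for the whole sample. It is relevant because Section 5.2 foresees ancillary analyses in all participants; under this mechanism a larger sample makes a false interaction more likely to be declared. The mean unadjusted arm effect was 0.50 in every setting.

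**Unequal arm means.** Suppose r = 0.3 in both arms, but assignment shifts the variable by 0.5 SD. Then E[Y | A, M] = 0.50A + 0.3(M − 0.5A) = 0.35A + 0.3M. There is no false interaction, but the effect within any level is 0.35, not 0.50. A separate simulation, with a latent prognostic factor, equal links to it in both arms and a 0.5 SD shift, gave 5.1% rejection at 64 per arm, in line with this.

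**The case against.** The strongest reply is that the plan commits to nothing wrong. The labels say only that these variables might be moderators, no hypothesis uses moderation, and Section 5.6 contains no moderator model. The rejection rates above 5% come from assumed unequal correlations, and no passage points to such a gap. Section 5.1 says aCDSMP is meant to account for non-specific elements, including positive expectancy.

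Most of this stands, and it limits the point to exploratory analyses. It does not remove it. The Section 5.5 labels are the only guidance the documents give on which variables may serve as moderators, and nothing in Section 5.6 restricts them. Matched expectancy bears on arm means; the illustration already sets those equal, and the false interaction still arises when the correlations differ.

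Three stronger readings go beyond the documents:
- A reader might infer that the trial means to use these interactions to pick out beforehand which Veterans benefit. No section says so.
- A reader might infer that the moderator label contradicts the Midpoint's mediation purpose. The Abstract's examples are mindfulness and self-efficacy; it does not mention credibility, and Section 5.5 lists mediators under a separate heading.
- A reader might take the Section 5.4 sentence on covariates to mean adjustment for care received after randomisation. Without a time point, it may equally mean care in place at entry.

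**Conclusion.** The point holds as a low-priority correction. Section 5.5 gives a moderator role to two variables that assignment and early response can affect. Interactions with them may therefore be false; the documents do not show that they will be.

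The size cannot be derived from the plan. Under the stated assumptions the interaction test runs from its nominal 5%, when the variable relates to outcome equally in both arms, to about 23% with 64 per arm at correlations 0.5 and 0.3. Equal correlations do not make the within-level effects sound: they are still biased if the arm means of the variable differ.

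A reader might infer that the primary result is at risk. It is not: the Hypothesis One comparison, unadjusted for these variables, remains a comparison of randomised groups.

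**What to change.** In Section 5.5, relabel Midpoint credibility/expectancy as a process measure compared descriptively by arm, and other care since baseline as descriptive by arm. In Section 5.6, add one sentence: moderator analyses, and any covariates adjusted for in the arm comparison, are limited to variables fixed before randomisation, such as the demographics and MINI SUD classification already listed. That sentence also settles the covariate wording in Section 5.4, so no separate edit or baseline chart search is needed there.

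Calling credibility a mediator and adjusting only for baseline symptoms would not be a sound substitute. It leaves confounding by symptom change between baseline and Weeks 4 to 5, which treatment may itself affect.

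The cost is two table labels and one sentence. All planned data are still collected and reported. The downside is that there would be no moderator analysis of expectancy or of later care.

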5.6 Data Analysis

We powered the study to detect a between group effect size Cohen's $d \geq 0.50$ for each of the primary outcome measures. An effect size $d = 0.5$ represents a medium effect, and a change smaller than $d=0.50$ has been advocated as a reasonable threshold of clinical significance when assessing patient reported outcomes, including pain and physical and emotional functioning.⁸ The literature (see section on MBIs for CMI), and our pilot data (preliminary studies section) suggest medium to large effect sizes for CMI, supporting the feasibility of detecting this level of difference. Although effect sizes derived from small samples are inherently unreliable,⁷ we included effect sizes from our pilot work as part of a broader review of the literature on outcomes of CMI symptoms after MBIs. As described above, the ability to detect a medium effect

size is supported by evidence of only modest effects in the proposed comparison condition. Overall, we think that powering the study to detect a difference of $d=0.50$ or greater between arms is conservative and clinically relevant.

Assuming a between group effect size of at least $d=.50$, equal allocation to either intervention, a two-sided $\alpha = 0.05$, and $\beta = 0.20$, at least 64 GW Veterans are required in each randomization arm.⁹⁷ To protect against the effects of attrition, we added 20% to this final sample size for a recruitment goal of 154 GW Veterans with CMI. This attrition estimate is conservative; it is slightly greater than in our pilot RCTs comparing MBSR to TAU.³ The sample size required *per arm* of the study (at 80% and 90% power) is presented across a range of effect sizes (Table 3).⁹⁷

Intraclass correlation (ICC): our pilot study of MBSR for GW Veterans (preliminary studies) showed an ICC for primary outcomes of $\rho= 0.00$ at follow-up. Because our data do not indicate significant ICCs for any of the primary outcome measures, the proposed analyses do not incorporate ICC results and are not powered to account for them.

Qualitative data will be coded (a sort of pre-analysis) continuously as participants complete their qualitative interviews; when saturation is reached, and no new codes are being generated, the research team will stop conducting the interviews and begin to analyze the qualitative data more extensively. The Project Manager and [name] will be primarily involved in the qualitative data analysis.

Quantitative data will be analyzed following the completion of the final assessments of the last subject cohort, which is projected to take place in the last six months of Year Four of the study. The dataset will be analyzed by [name], in consultation with [name].

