5.0 Study Procedures

5.1 Study Design

This study is a randomized controlled trial comparing Mindfulness-Based Stress Reduction (MBSR) with an active control, augmented Chronic Disease Self-Management Program (aCDSMP), to assess the efficacy of MBSR for Gulf War Veterans with Chronic Multi-symptom Illness (CMI). GW Veterans (n=154) with CMI will be randomized to either 8 weeks of MBSR (n=77) or aCDSMP (n=77). All participants will complete assessments at baseline, immediately post-treatment, as well as at 3-months and 6-months post-treatment. They will also complete a short Midpoint assessment halfway through the class series.

Brief semi-structured interviews will also be included in the MBSR/CDSMP assessments of the Gulf War veterans at the post-test time to collect data for qualitative analysis. The qualitative analysis will be conducted to develop a more complete understanding of the acceptability and satisfaction with MBSR and aCDSMP by GW Veterans. These interviews will be conducted on a subset of GW Veterans who either complete or fail to complete (attend fewer than 4 class sessions) for both MBSR and CDSMP. For Veterans who discontinue treatment, interviews will be conducted within

two weeks of discontinuation. Interviewers will be provided interview training specific to this study methods by [name]. Data will be catalogued using Atlas.ti software system where upon the data cleaning and quality assurance process will be conducted to assure creditability and trustworthiness. [name] will conduct a comparison of the notes, taped interviews and transcripts to assess the following: interview protocol adherence, creditability of memos and notes, and detection of leading questions and produce a quality assurance report that will be presented to the research team members.

A comprehensive outline of the various data collection tools/measured to be administered at each of the four assessments is provided in **Section 5.5 Study Evaluations.**

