The primary mechanism of recruitment of GW Veterans will be letters and a pamphlet sent to Veterans with an indicator in the hospital database that their period of service was the Persian GW, and who were at least 18 years old in August 1990. We also will access the Gulf War Registry to recruit Veterans known to be deployed during the Gulf War. The letter will inform veterans that they may receive up to 3 calls from study staff members inviting them to participate in the study. If they do not wish to receive study contact, they may contact the study coordinator and they will not receive any further study contact. The list of potentially eligible Persian GW Veterans will be generated using a VistA/fileman query or a VINCI query; this meets the approval of our local IRB. If they respond to the letter, they will be screened by telephone for inclusion criteria, which will be confirmed at an in-person baseline visit. Using this method, in our pilot trial of MBSR for GW Illness (see preliminary studies) *we successfully recruited 6-8 GW Veterans per month – a rate higher than the proposed trial.* Over a 1.5 year time period we recruited and randomized 55 GW Veterans with CMI; we developed the methodology to send letters *midway* through this pilot project; upon initiation of this method of recruitment, it markedly increased our enrollment rates. Currently, we are applying the same recruitment methodology to a CSR&D trial for Veterans with PTSD, which has resulted in recruitment of approximately 2-5 Veterans per week (we have about a 4% response rate for letters, and half of those (2% of letters sent) pass a phone screen for eligibility). Extrapolating to this proposal, we would need to send out 7,700 letters to recruit 154 GW Veterans. We performed a data pull as preparation for this proposal, and found that there are 30,452 unique Veterans with a period of service of 'Persian GW' who received care at VAPSHCS in FY14 and were at least 18 years old at the time of GW I (August, 1990). Thus, the recruitment goals are feasible.

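### 77 per arm keeps the required 64 only if attrition is at most 16.9%, not the plan's own 20%; at 20%, completers-only power is about 79%, a small shortfall

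*Combined protocol and SAP*

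**What the plan says.** Section 5.6 (Data Analysis) bases the sample size on a between-group effect of d = 0.50, 1:1 allocation, two-sided alpha 0.05 and 80% power, and concludes that "at least 64 GW Veterans are required in each randomization arm". It then makes the allowance for dropout: "we added 20% to this final sample size for a recruitment goal of 154 GW Veterans with CMI". The sentence after that describes what the 20% is: "This attrition estimate is conservative; it is slightly greater than in our pilot RCTs comparing MBSR to TAU". The pilot attrition rate itself is not given.

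The resulting 154, or 77 per arm, is used elsewhere. The Abstract and section 5.1 (Study Design) give it as the number of GW Veterans to be randomized, section 5.2 (Recruitment Methods) as the GW part of the recruitment goal, and the mailing estimate in 5.2 rests on it: "we would need to send out 7,700 letters to recruit 154 GW Veterans". Section 5.2 also states that Veterans from other service periods do not count towards power for the primary hypotheses. Hypothesis One in section 3.0 places the primary comparison at the 6-month follow-up.

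**The concern.** Attrition is a fraction of those randomized. To keep a required number after a given fraction is lost, the required number is divided by one minus that fraction. The plan instead multiplies by one plus the fraction, which covers a smaller loss than the one it names.

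Three statements in 5.6 therefore do not fit together: a minimum of 64 per arm, a target of 77 per arm, and a 20% attrition estimate described as conservative. A reader would take the target to hold 64 per arm, and so 80% power, if one participant in five is lost. It does not. The whole primary sample size rests on this figure. The primary comparison is at the last assessment, where cumulative loss is greatest, and 64 is the smallest whole number per arm that reaches 80% power, so there is almost no slack.

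**Working it through.** **Inputs.** All are from section 5.6 except the 77 per arm, which is in the Abstract and 5.1: d = 0.50; 1:1 allocation; two-sided alpha 0.05; power 80%; 64 per arm required; 20% attrition; 77 per arm randomized. The analysis is taken to be an unadjusted two-sample t-test in completers, because that calculation reproduces the plan's 64 and the available text names no primary model.

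**Step 1: reproduce the plan.**
- Two-sample t-test, 80% power: n = 63.77 per arm, rounded up to 64. This agrees with the plan.
- Multiplicative inflation: 64 × 1.20 = 76.8, rounded up to 77 per arm; 2 × 77 = 154. This agrees with the plan.
- Inflation by division: 64 / (1 − 0.20) = 80 per arm; 2 × 80 = 160. This does not give 154, so the plan multiplied.

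**Step 2: attrition that 77 per arm can absorb.**
- Tolerable losses: 77 − 64 = 13 per arm.
- Break-even attrition: 13 / 77 = 16.9%.

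**Step 3: what remains at 20%.**
- Losses: 0.20 × 77 = 15.4 per arm.
- Remaining: 77 × 0.80 = 61.6 per arm, about 123 in total, against 64 and 128.

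**Step 4: effect on power** (noncentral t, d = 0.50, two-sided 0.05).

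| Completers per arm | Power |
|---|---|
| 61 | 78.2% |
| 61.6 | 78.6% |
| 62 | 78.9% |
| 64 | 80.1% |
| 77 (no loss) | 86.9% |

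The normal approximation gives 79.2% at 61.6 per arm.

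With 77 randomized per arm, power by assumed attrition is:

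| Attrition | Power |
|---|---|
| 15% | 81.0% |
| 17% | 80.1% |
| 18% | 79.6% |
| 20% | 78.6% |

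**Step 5: detectable effect at 80% power.** d = 0.499 with 64 per arm and d = 0.509 with 61.6 per arm.

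**The case against.** The strongest reply is that the plan did literally what it says. It added 20% to 64 and never states that 64 remain after a 20% loss, so the fault is loose wording and not a wrong sum. That is true of the addition. It does not cover the next sentence, which calls the 20% an attrition estimate and sets it beside pilot attrition. Even read as a plain recruitment margin, the text nowhere says that the margin covers only a 16.9% loss.

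Second, the 20% is presented as cautious, so the expected loss is lower, and at 16.9% or below nothing is lost. This may be so, but the pilot rate is not reported. A rate of 17% to 19% would also be slightly under 20%, and at any rate in that range fewer than 64 per arm remain.

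Third, the 78.6% depends on an assumed analysis. The three symptom outcomes are measured at baseline and four later points, and a baseline-adjusted model would recover the deficit with little correlation: r² = 1 − 61.6/64 = 0.0375, so r is about 0.19. This stands as a reason to think that the practical loss may be nil. It does not remove the point, because the available text commits to no such model and the plan's own 64 takes no credit for one.

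Fourth, section 5.2 gives the GW share as at least half of 308, so 154 could be read as a floor. The Abstract and 5.1 nonetheless state 154 and 77 flatly, and it is 154 that the power argument uses.

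Last, a loss of about 1.4 points of power decides nothing about the design. That is a fair statement of its size, and it is why the remedy is a restatement and not more recruitment.

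**Conclusion.** The concern holds. As written, 154 GW Veterans do not keep the plan's own minimum of 64 per arm at the plan's own attrition rate. They do so only up to 16.9%.

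The consequence is small: at 20% attrition the sample falls short by about 2.4 completers per arm (64 − 61.6), and power is about 79% where the plan intends 80%. It arises only if attrition exceeds 16.9%.

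The break-even rate and the 61.6 follow from the plan's figures alone. The power figures also assume an unadjusted completers-only t-test and, as the plan does, no clustering by group.

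**What to change.** In 5.6, replace the inflation sentence with one that states what the target delivers, for example:

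> We will recruit 154 GW Veterans (77 per arm). This retains the required 64 per arm if attrition is at most 16.9%; at 20% attrition about 61–62 per arm remain, giving about 79% power for d = 0.50 (two-sample t-test, completers only), or 80% power for d = 0.51.

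The words in parentheses give the basis of the power figure; if they might be read as naming the primary analysis, add that they apply to the sample size calculation only. The sentence on conservatism that follows should then give the pilot attrition rate, so that it can be compared with 16.9%.

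The cost is this edit to one paragraph. The figures 154, 77 and 308 stay as they are.

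Raising the GW target to 160 is optional and not needed for the correction. It would make 77 into 80 per arm in the Abstract and 5.1, with conforming edits in 5.2. At the 2% yield stated in 5.2, the mailing becomes 160 / 0.02 = 8,000 letters instead of 7,700. Within 308, the non-GW number becomes 308 − 160 = 148 instead of 154.
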